6.1.5. End of Study Activity: Product Preference Questionnaire

After applying the two foam Hand Sanitizers A and B, the participant will complete a Product Preference Questionnaire. Participant responses to the questionnaire will be recorded in the CRF by study staff. When both Hand Sanitizers A and B have been applied and the participant has completed the study VAS Assessments and the Product Preference Questionnaire, the participant will be dismissed from the study.

7. ADVERSE EVENTS (AEs)

7.1. Definition of AE

The FDA definition for an AE is: An AE is any unfavorable and unintended sign (including an abnormal laboratory finding), symptom, or disease temporally associated with the use of a medical treatment or procedure that may or may not be considered related to the medical treatment or procedure.

However, a narrower definition of AE will be used for this study. In this study, an AE is any untoward medical occurrence related to the topical use of the hand sanitizers during this study, including skin itching, erythema, edema, or any other skin irritation that occurs.

7.2. Definition of Serious Adverse Event (SAE)

The FDA definition of a SAE will be used in this study: An AE or suspected adverse reaction is considered "serious" if, in the view of either the PI or sponsor, it results in any of the following outcomes:

- Death,
- A life-threatening adverse event,
- Inpatient hospitalization or prolongation of existing hospitalization,
- A persistent or significant incapacity or substantial disruption of the ability to conduct normal life functions, or
- A congenital anomaly/birth defect.

Important medical events that may not result in death, be life-threatening, or require hospitalization may be considered serious when, based upon appropriate medical judgment, they may jeopardize the participant and may require medical or surgical intervention to prevent one of the outcomes listed in this definition. All SAEs will be reported to Medline, regardless of potential relationship to the study product(s). SAEs will be reported to the reviewing IRB as necessary according to their reporting requirements.

7.3. Severity of AE

The severity of all AEs will be graded on a scale of one through five according to the Common Terminology Criteria for AE guideline, where each grade represents a unique clinical description based on this general guideline:

• **Grade 1:** Mild; asymptomatic or mild symptoms; clinical or diagnostic observation only; intervention not indicated.

MED-2022-DIV60-001 18-NOV-2022 Version 3.0

- **Grade 2:** Moderate; minimal, local or noninvasive intervention indicated; limited age-appropriate instrumental activities of daily living.
- **Grade 3:** Severe or medically significant but not immediately life-threatening; hospitalization or prolongation of hospitalization indicated; disabling; limiting activities of daily living involving self-care.
- Grade 4: Life threatening consequences; urgent intervention indicated
- **Grade 5:** Death related to AE

7.4. Relatedness of AE and SAE

- Unrelated: This category applies to those AEs which, after careful consideration, are clearly and incontrovertibly due to extraneous causes (disease, environment, etc.)
- **Possible:** This category applies to those AEs for which, after careful medical consideration at the time they are evaluated, a connection with the Investigational Product administration appears unlikely but cannot be ruled out with certainty.
- **Probable:** This category applies to those AEs which, after careful medical consideration at the time they are evaluated, are felt with a high degree of certainty to be related to the study product(s).
- **Definite:** This category applies to those AEs which, after careful consideration, are clearly and incontrovertibly due to the study product(s).

7.5. Expectedness

The PI will be responsible for determining whether an AE or SAE is expected or unexpected. An AE will be considered unexpected if the nature, severity, or frequency of the event is not consistent with the risk information previously described for the study intervention.

7.6. AE Reporting

The AEs will be recorded on the AE form (provided by Medline Industries, LP) by the study staff and reviewed by the PI. Changes in the severity of an AE will be documented to allow an assessment of the duration of the event at each level of severity. Changes in severity will necessitate a new CRF to document the new level of severity. AEs characterized as intermittent require documentation of onset and duration of each episode.

Non-serious AEs will be reported to the study sponsor on a monthly basis for review or as agreed upon with the study sponsor, and reported to the IRB per IRB reporting requirements.

7.7. SAE Reporting

The PI shall complete an SAE Form (provided by Medline Industries, LP) and submit to the study sponsor as soon as possible, but in no event later than 48 hours after the PI first learns of the effect. The PI will be responsible for reporting the event to the IRB, if applicable, per the IRB's reporting requirements. The study sponsor is responsible for conducting an evaluation of the SAE and shall report the results of such evaluation to the FDA and to all reviewing IRBs, if applicable, within 10 working days after the sponsor first receives notice of the effect. Thereafter, the sponsor shall submit such additional reports concerning the effect as FDA requests.

For questions regarding this process or the event, you may contact your Medline clinical designee or the Medline Director of Clinical Operations:

Name: [name] RN, BSN, CCRA

[contact]

E-mail: [contact]

8. STATISTICAL CONSIDERATIONS

8.1. Sample Size Determination

Sample size N of 90 (45 for a foam cohort and 45 for a gel cohort to be evaluated in a future study) was estimated to provide 80% power at the 95% level of significant for the proportion of HCW preferring one gel/foam product over the competing gel/foam product using the "Non-Inferiority Tests for the Difference Between Two Correlated Proportions" procedure in PASS 2021 Power Analysis and Sample Size Software (2021). NCSS, LLC. Kaysville, Utah, USA, ncss.com/software/pass. The estimated non-inferiority margins were .03 to .08 with estimated proportion differences of .1, .15 and .20. This study will utilize the sample of N=45 for the foam cohort.

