3. OBJECTIVES AND ENDPOINTS

OBJECTIVES	ENDPOINTS	JUSTIFICATION FOR ENDPOINT(S)
Primary		
1. To establish the non-inferiority of the Spectrum product to the Purell product by comparing the foam hand sanitizers with regard to the user touch and feel experience and overall acceptability.	1. The user touch and feel experience of the hand sanitizer products evaluated by VAS assessments of HCWs overall satisfaction and moisturization, and HCWs assessment of product preference.	To evaluate the HCW user touch and feel experience of the products and compare product preference between the foam hand sanitizer products.

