8.2. Randomization

The order in which the participants test a hand sanitizer product first or second will also be randomly assigned. The participants, as well as on-site staff will be blinded to testing products. If a participant is unable to complete the study or has missing data, the participant will be replaced such that the new participant will be assigned to the randomization cohort of the replaced participant. Randomization schedule will be generated using SAS® software, Version 9.4 of the SAS System for Windows. Copyright © 2013 SAS Institute Inc.

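### The 80% power for non-inferiority on preference holds only under an unstated Spectrum lead of 10 to 20 points; power at equal preference is not given, and the named preference test has no margin

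*Combined protocol and SAP*

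**What the plan says.** Section 3 sets a single primary objective: "To establish the non-inferiority of the Spectrum product to the Purell product". Preference is one of three endpoint components, beside VAS overall satisfaction and VAS moisturization, and it is the only one used for sizing.

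Section 8.1, repeated in the synopsis (1.1), says that the sample "was estimated to provide 80% power at the 95% level of significant for the proportion of HCW preferring" one product over its competitor. The procedure was "Non-Inferiority Tests for the Difference Between Two Correlated Proportions". The scenarios are given in one sentence: "The estimated non-inferiority margins were .03 to .08 with estimated proportion differences of .1, .15 and .20". The total of 90 covers a foam and a gel cohort, and for this trial "This study will utilize the sample of N=45 for the foam cohort".

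Neither section gives the direction of the differences, a single margin, the sidedness, the discordant proportion, or power at a zero difference. Section 8.4.2 compares preference proportions with the McNemar test or another suitable method. It names no margin, confidence interval or order of claims.

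**The concern.** A colleague who reads 80% power for non-inferiority is likely to expect a good chance of success if the two foams are about equally liked. The listed scenarios do not cover that case. All of them place the true difference further from zero than any margin, so the figure describes a trial in which one product is clearly preferred.

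Two things are at stake. The sponsor may not see how weak the preference comparison is when the foams are similar, and a failed test could then be taken as a finding against Spectrum. Also, having assumed a lead, the plan sets no rule for concluding either non-inferiority or superiority from the preference data.

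**Working it through.** **Inputs.** From 8.1: n = 45, margins m = .03 to .08, differences d = .10, .15, .20, power 80%. From 8.2: "If a participant is unable to complete the study or has missing data, the participant will be replaced", so 45 analysed participants is taken as given. Not in the documents, and therefore assumed over a range: the discordant share p (participants whose answers separate the two products), from .10 to 1.0, where 1.0 is a forced choice; and one-sided alpha of 5%, with 2.5% as the alternative.

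**Formula.** With d = Spectrum minus Purell, by normal approximation for paired proportions:

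power = Φ[(d + m) / √((p − d²)/45) − z], with z = 1.645 (5%) or 1.960 (2.5%).

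**Step 1: the plan's 80%.** Solving for p gives p = 45·[(d + m)/(z + 0.842)]² + d². At one-sided 5%, m = .08, d = .20: 45 × (.28/2.487)² + .04 ≈ .61. The discordant share at which power is exactly 80% (a larger share gives less power) is:

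| | d = .10 | d = .15 | d = .20 |
|---|---|---|---|
| m = .03 | .13 | .26 | .43 |
| m = .08 | .25 | .41 | .61 |

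At one-sided 2.5% the rows become .11, .21, .34 and .20, .33, .49. The 80% is reachable for some combinations and not for others. With forced choice the best case (m = .08, d = .20, 5%) is Φ(.28/√(.96/45) − 1.645) = 61%. Without p, the sidedness and the margin–difference pair, the stated figure can be neither reproduced nor refuted.

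**Step 2: direction.** If the differences run against Spectrum, each lies beyond each margin. The most favourable such case checked is d = −.10, m = .08, p = 1.0: Φ(−.02/√(.99/45) − 1.645) = 3.8%. Only a Spectrum lead is compatible with 80%.

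**Step 3: equal preference (d = 0).** The formula becomes Φ(m/√(p/45) − z). Two ends at 5%: m = .03, p = 1.0 gives Φ(.201 − 1.645) = 7%; m = .08, p = .20 gives Φ(1.200 − 1.645) = 33%.

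| Discordant share | m = .03, 5% | m = .08, 5% | m = .03, 2.5% | m = .08, 2.5% |
|---|---|---|---|---|
| .10 | 16% | 52% | 9% | 40% |
| .20 | 12% | 33% | 7% | 22% |
| .50 | 9% | 19% | 5% | 11% |
| 1.0 | 7% | 13% | 4% | 8% |

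Exact multinomial power for the score test at 5% and m = .08 is 44%, 31%, 19% and 12% down the rows, so the approximation is slightly generous at low discordance. For 80% power at d = 0 and one-sided 5%, n = p·(2.487/m)². With p = .20 this is 194 for m = .08 and 1,374 for m = .03.

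**Step 4: the named test.** McNemar's null is a difference of zero; the objective's null is a difference at or below −m. A non-significant McNemar result does not show non-inferiority. A significant one in Spectrum's favour would imply it, but only by clearing the higher bar. The two bars differ: at d = .20, p = .30 and one-sided 5%, the same normal approximation gives 84% power against zero, 92% against m = .03 and 98% against m = .08.

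**The case against.** Sizing a non-inferiority comparison on an expected advantage is a permissible choice, and the plan does not claim power at equality. That stands: the fault is that the lead is left unstated and unsupported, not that it was assumed.

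Three stronger readings are tempting, and the documents do not support them.

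- **That the plan has no way to detect a Spectrum lead.** McNemar in 8.4.2 tests against equality and can detect one. What is missing is a test against a margin and a prespecified order of claims. The allowance for other methods leaves room for a margin-based test but does not specify one.
- **That the preference test would mostly fail if the foams are equally liked, whatever the data look like.** This depends on a discordant share that is not stated. At margin .08 and one-sided 5%, power at equality is 52% with 10% discordant and 78% with 5%. Such shares mean that 90% to 95% of participants do not separate the products. That seems unlikely for a preference questionnaire, but the response options are not in the text and it cannot be excluded.
- **That 60% to 62% of participants must choose Spectrum.** Exact pass marks of 28 of 45 (margin .03) and 27 of 45 (margin .08), against 29 of 45 for superiority, hold only for a forced choice at one-sided 5%. At 2.5% they are 29, 28 and 30. Under forced choice, power at equality is 7% to 13%, so these marks cannot be combined with the 33% figure.

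It is also fair that preference is only one of three endpoint components. The point says nothing about power for the VAS scores.

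**Conclusion.** The point holds in this form. The documents fix the margins and the differences, and these imply that the 80% applies only if Spectrum is truly preferred by 10 to 20 points. That direction is an inference, but the opposite sign gives at most about 4% power.

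At equal preference with N=45 and one-sided 5%, power is about 7% to 12% for margin .03 and 13% to 33% for margin .08, provided at least 20% of participants are discordant. It is lower at one-sided 2.5% and higher if discordance is below 20%. None of this shows that the stated 80% is wrong; it shows which truth it depends on. Section 8.4.2 adds a separate gap: no decision rule ties the preference data to the non-inferiority objective. Both should be corrected, because the second changes what the trial can conclude.

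**What to change.** 1. In 1.1 and 8.1, say that the 80% holds only under an assumed Spectrum lead and give the reason for that lead. Name one margin, the sidedness and the discordant share, and report the power at a zero difference under those same values.
2. In 8.4.2, base the preference decision on a confidence interval for the paired difference, Spectrum minus Purell, at the stated alpha. Declare non-inferiority if the lower limit lies above minus the margin. If it does, declare superiority if the same lower limit lies above zero. Because the order is fixed, no alpha adjustment is needed within the preference endpoint; this does not settle multiplicity across preference and the two VAS scores.
3. In 8.4.2, add that failure to show non-inferiority at this sample size is not evidence that Spectrum is inferior.

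The cost is wording in three places and a less favourable-looking power statement. No extra participants or procedures are needed.

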8.2. Randomization

The order in which the participants test a hand sanitizer product first or second will also be randomly assigned. The participants, as well as on-site staff will be blinded to testing products. If a participant is unable to complete the study or has missing data, the participant will be replaced such that the new participant will be assigned to the randomization cohort of the replaced participant. Randomization schedule will be generated using SAS® software, Version 9.4 of the SAS System for Windows. Copyright © 2013 SAS Institute Inc.

8.3. Populations for Analyses

The analyses will be performed on the intent-to-treat population which consists of all subjects who were qualified for entry criteria and adhered to the protocol, meaning completing the satisfaction and user experience questionnaire for both testing products.

No per protocol, safety, or other analyses groups are planned.

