1.1. Schedule of Activities (SOA)

Required Study Activities and Assessments	Visit 1
Verification of Eligibility	X
Participant Washes Hands and Waits Minimum 2 Minutes	X
Study Staff Times Participant for 2 Minute Waiting Period After Hand Washing	X
Application of Hand Sanitizer A	X
User Touch and Feel VAS Assessment	X
Participant Washes Hands and Waits 2 Minutes	Х
Study Staff Times Participant for 2 Minute Waiting Period After Hand Washing	X
Application of Hand Sanitizer B	X
User Touch and Feel VAS Assessment	X
Product Preference Questionnaire	X
Participant Dismissal	X
Adverse Events	X

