6.1.2. Participant Cohort Randomization

Participants will be assigned to evaluate two foam hand sanitizers. The order in which the participants test a hand sanitizer product first or second will be randomly assigned. The participants, as well as on-site staff will be blinded to testing products. If a participant is unable to complete the study or has missing data, the participant will be replaced such that the new participant will be assigned to the randomization cohort of the replaced participant. Randomization schedule will be generated using SAS® software, Version 9.4 of the SAS System for Windows. Copyright © 2013 SAS Institute Inc.

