8.4. Statistical Analysis

Descriptive and/or summary statistics will be calculated for the primary endpoints, which are the user touch and feel experience of the hand sanitizer products evaluated by visual analog scale assessments of HCWs overall satisfaction and moisturization, and HCWs assessment of product preference. Statistical analyses will be conducted in SAS® software, Version 9.4 or higher of the SAS System for Windows (Copyright © 2013 SAS Institute Inc.) or other appropriate statistical software.

All continuous variables will be summarized using the following descriptive statistics: n (non-missing sample size), mean, standard deviation, median, maximum and minimum. The frequency and percentages (based on the non-missing sample size) of observed levels will be reported for all categorical measures. In general, all data will be listed, sorted by site, treatment and subject, and when appropriate by visit number within subject. All summary tables will be structured with a column for each treatment in the order (Control, Experimental) and will be annotated with the total population size relevant to that table/treatment, including any missing observations.

All protocol deviations will be recorded and examined for potential bias in accordance with section 9.

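### Section 8.3 confines every analysis to completers of both questionnaires and plans no safety group, so any AE rate would omit someone who reacted and stopped early

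*Combined protocol and SAP*

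**What the plan says.** Section 8.3 sets one population for the analyses. It is labelled intention-to-treat, but membership requires eligibility and adherence, the latter defined as "meaning completing the satisfaction and user experience questionnaire for both testing products". No exception is made for AEs, and the section closes with "No per protocol, safety, or other analyses groups are planned".

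Section 6.1.2 states: "If a participant is unable to complete the study or has missing data, the participant will be replaced". Section 8.2 repeats the rule, and in both places the replacement takes over the randomisation cohort of the person replaced.

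AEs appear in the Schedule of Activities under "Required Study Activities and Assessments". Section 7.1 narrows the AE definition to untoward occurrences related to topical use of the sanitizers, and section 2.3.1 names minor skin irritation as the possible harm. On handling, section 7.6 has AEs recorded on a form and reviewed by the PI, and states: "Non-serious AEs will be reported to the study sponsor on a monthly basis for review" (or on another agreed schedule).

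Section 8.4 directs summary statistics to the primary endpoints, which are the VAS scores and product preference. It also gives a general rule that frequencies and percentages are reported for all categorical measures. On listings it says: "In general, all data will be listed, sorted by site, treatment and subject". Of summary tables it says that they "will be annotated with the total population size relevant to that table/treatment, including any missing observations".

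**The concern.** An analysis set for harms should contain everyone exposed, because leaving the study early can itself be a consequence of harm. Here the only set requires both questionnaires to be completed. A participant who applies the first product, develops irritation and declines the second has been exposed and has had exactly the kind of event that section 7.1 defines, yet falls outside the set and is replaced by someone else. Exclusion can therefore depend on the safety outcome.

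What is at stake is narrow. If the clinical study report gives an AE percentage, that percentage could be lower than its own AE listing implies, for example no AEs in the table and one in the listing. Safety is not a study objective. The VAS and preference analyses, AE reporting and AE-based stopping do not depend on this point.

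**Working it through.** The plan states no AE rate, so there is no figure to reproduce. The check has two parts.

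**1. Reading the sections together.** Follow a participant who applies Hand Sanitizer A, reacts and stops.

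- Sections 7.6 and 8.4: the AE is recorded, reviewed, reported and, in general, listed.
- Section 8.3: the second questionnaire is missing, so the participant is outside the only analysis population.
- Sections 6.1.2 and 8.2: the participant is replaced, and recruitment continues until 45 have completed.
- Section 8.4: the general rule on categorical measures could yield an AE percentage. The annotation rule leaves room for an exposed denominator but does not set one, and 8.3 rules out the group that would supply it.

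A participant who reacts but completes both questionnaires stays in the 8.3 set and is counted.

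**2. Size.** The 45 completers come from section 8.1. All other inputs are assumptions, because the documents give no irritation or drop-out rate:

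- m = completers with an AE
- j = participants who applied a product, reacted and stopped
- k = participants who applied a product and stopped without an AE
- p = probability that a participant reacts and stops before the second questionnaire

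Rate on the 8.3 set: m/45. Rate among all exposed: (m + j)/(45 + j + k).

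| m | j | k | 8.3 set | All exposed |
|---|---|---|---|---|
| 0 | 0 | 0 | 0/45 = 0% | 0/45 = 0% |
| 0 | 1 | 0 | 0/45 = 0% | 1/46 = 2.2% |
| 0 | 2 | 0 | 0/45 = 0% | 2/47 = 4.3% |
| 1 | 1 | 0 | 1/45 = 2.2% | 2/46 = 4.3% |
| 1 | 2 | 0 | 1/45 = 2.2% | 3/47 = 6.4% |
| 1 | 0 | 1 | 1/45 = 2.22% | 1/46 = 2.17% |
| 1 | 1 | 1 | 1/45 = 2.2% | 2/47 = 4.3% |

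Early stops without an AE push the other way, but only slightly: 2.22% − 2.17% = 0.05 percentage points for one such stop.

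To see how often j exceeds zero, treat participants as independent, ignore stops for other reasons, and recruit until 45 complete. The number of stops is then negative binomial:

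- P(j ≥ 1) = 1 − (1 − p)^45
- P(j ≥ 2) = 1 − (1 − p)^45 × (1 + 45p)

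| Assumed p | P(j ≥ 1) | P(j ≥ 2) |
|---|---|---|
| 0.1% | 4.4% | 0.1% |
| 0.5% | 20.2% | 2.2% |
| 1% | 36.4% | 7.8% |

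For p = 1%: 0.99^45 = 0.6362, so P(j ≥ 1) = 0.364; and 0.6362 × 1.45 = 0.9225, so P(j ≥ 2) = 0.078.

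**The case against.** The strongest reply is that the plan contains no analysis to which this applies. Section 8.4 aims its statistics at the primary endpoints, 8.4.1 to 8.4.3 cover VAS scores, preference and demographics, and section 3 has no safety objective. A plan with no safety analysis that says it has no safety group is consistent with itself. The general rule on categorical measures is a weak bridge: it may describe only the grades of the AEs that occur, and it works on the non-missing sample size. With 45 participants, a listing shows every event, and whoever writes an AE table could use the section 8.4 annotation rule to give an exposed denominator. Finally, every stop rate above is assumed, and the documents point to low values: marketed products, exclusion of skin conditions and known allergies, one visit of about an hour, and about 1 mL of each product.

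Most of this stands, and it is why the point is conditional and minor. What it does not answer is that 8.3 states a rule rather than leaving a gap. If an AE percentage is produced, the plan supplies only the completer denominator and expressly declines the alternative.

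A reader might go further and infer that reactions in early stoppers go unrecorded or are hidden from the sponsor. The documents do not support that: recording and reporting under section 7 do not depend on completing the questionnaires. Nor do they support saying that the study will understate its AE rate, since no rate is specified and there may be no early stop.

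**Conclusion.** The point holds as a conditional, minor one. If AEs are tabulated under section 8.3 as written, participants who reacted and stopped are left out of numerator and denominator. With no AE among completers, one such person makes the difference between 0/45 and 1/46 (2.2%), and two between 0/45 and 2/47 (4.3%). If nobody stops early, which is likely, there is no effect at all.

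The reading of 8.3 with 6.1.2 and 8.2 rests on the text alone. The counts and probabilities rest on assumed stop rates and on independence between participants; they show the scale and are not forecasts. This point does not bear on whether the completer set suits the VAS and preference comparisons.

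**What to change.** In section 8.3, replace the closing sentence on analysis groups with:

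> Any AE summary will include all participants who applied at least one product, including those later replaced; overall figures use all such participants as the denominator and by-product figures use the number who applied that product. No per protocol or other analysis groups are planned.

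Both denominators are needed. Someone who stops after the first product makes 46 exposed overall and 46 for that product, but leaves 45 for the other.

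If AEs are summarised, the number and percentage of participants with any AE, overall and by last product applied before onset, is enough. By-product figures should stay descriptive, because a delayed reaction to the first product may be attributed to the second.

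The cost is one changed sentence, with no extra participants, visits, procedures or required tables. The downside for the sponsor is a possibly slightly less favourable AE rate.
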